6.1.2 TITRATION AND MAINTENANCE PERIODS

6.1.2.1 Titration Period Study Day 1

Subjects will take their second dose of study medication on the morning of Study Day 1. Study Day 1 is considered the first day of dosing, even though subjects received an in-clinic dose on Study Day -1.

6.1.2.2 Phone Visits 4 and 5 (Titration Period Study Days 4 and 8)

Site personnel will contact the subject via telephone on Titration Period Study Days 4 and 8 and record the following:

- AEs
- AESI
- Concomitant medications

In addition, site personnel will review study medication dosing procedure and the diary entries with the parent/caregiver.

6.1.2.3 Clinic Visit 6 (Titration Period Study Day 15)

Subjects will report to the clinic in the morning on Titration Period Study Day 15. The following procedures will be performed:

- Review current seizure activity (number/type/duration) from diary since previous visit
- Record concomitant medications
- Obtain weight
- Obtain vital signs
- Collect, review, and dispense diary. Ensure diary is being completed daily; if diary compliance is low (i.e. <90%), re-train parent/caregiver.
- C-SSRS Since Last Visit Assessment (Appendix 2)
- Clinical Global Impression – Improvement (assessed by parent/caregiver)
- Clinical Global Impression – Improvement (assessed by investigator)
- Record AEs
 - Perform an abbreviated physical and/or neurological examination as appropriate based on last exam and reported AEs
 - Collect plasma sample for AED pharmacokinetic evaluation if clinically indicated (must document time of last dose)
- Record AESI
- Collect used, partially used and unused study medication; perform drug accountability and review with parent/caregiver
- Dispense study medication

6.1.2.4 Phone Visit 7 (Maintenance Period Study Day 29)

Site personnel will contact the subject via telephone on Maintenance Period Study Day 29 and record the following:

- AEs
- AESI
- Concomitant medications

ZX008 (Fenfluramine Hydrochloride)**ZX008-1601 Clinical Study PA 4.0 (Japan) 25 July 2022**

In addition, site personnel will review the diary entries with the parent/caregiver. Ensure diary is being completed daily; if diary compliance is low (i.e. <90%), re-train parent/caregiver.

6.1.2.5 Clinic Visit 8 (Maintenance Period Study Day 43)

- Subjects will report to the clinic in the morning on Maintenance Period Study Day 43. Subjects should not take their morning dose(s) of study medication. The following procedures will be performed:
- Review current seizure activity (number/type/duration) from diary since previous visit
- Record concomitant medications
- Obtain weight (**Note: if the subject's weight is $\pm 25\%$ of the weight at Study Day-1, the IMP dose will be recalculated**)
- Obtain vital signs
- 12-lead electrocardiogram
- Doppler ECHO (this must be obtained any time between Study Day 40 and Study Day 54)
- Urine or serum pregnancy test for females of child-bearing potential
- Laboratory evaluation (serum chemistry, hematology, immunoglobulin hormones, and urinalysis (urine for urinalysis may be collected at home, the night before the clinic visit, as long as collection procedures are followed to maintain sample stability))
- Urine or serum THC panel
- Whole blood CBD
- Collect plasma sample for ZX008 pharmacokinetic evaluation at the following timepoints: within 1 hour prior to the morning dose of study medication, and 1, 2 and 4-6 hours after the morning dose of study medication
- Collect plasma sample for AED pharmacokinetic evaluation (must document time of last dose)
- Collect, review, and dispense diary. Ensure diary is being completed daily; if diary compliance is low (i.e. <90%), re-train parent/caregiver.
- C-SSRS Since Last Visit Assessment ([Appendix 2](#))
- Zarit Caregiver Burden Inventory ([Appendix 8](#))
- Clinical Global Impression – Improvement (assessed by parent/caregiver)
- Clinical Global Impression – Improvement (assessed by investigator)
- Perform an abbreviated physical and/or neurological examination as appropriate based on last exam and reported AEs
- Record AESI
- Collect used, partially used and unused study medication; perform drug accountability and review with parent/caregiver
- Dispense study medication

6.1.2.6 Phone Visit 9 (Maintenance Period Study Day 57)

Site personnel will contact the subject via telephone on Maintenance Period Study Day 57 and record the following:

- AEs
- AESI

ZX008 (Fenfluramine Hydrochloride)
ZX008-1601 Clinical Study PA 4.0 (Japan) 25 July 2022

- Concomitant medications

In addition, site personnel will review the diary entries with the parent/caregiver. Ensure diary is being completed daily; if diary compliance is low (i.e. <90%), re-train parent/caregiver.

6.1.2.7 Clinic Visit 10 (Maintenance Period Study Day 71)

Subjects will report to the clinic on Maintenance Period Study Day 71. The following procedures will be performed:

- Review current seizure activity (number/type/duration) from diary since previous visit
- Record concomitant medications
- Obtain weight
- Obtain vital signs
- Collect, review, and dispense diary. Ensure diary is being completed daily; if diary compliance is low (i.e. <90%), re-train parent/caregiver.
- C-SSRS Since Last Visit Assessment ([Appendix 2](#))
- Clinical Global Impression – Improvement (assessed by parent/caregiver)
- Clinical Global Impression – Improvement (assessed by investigator)
- Record AEs
- Perform an abbreviated physical and/or neurological examination as appropriate based on last exam and reported AEs
- Collect plasma sample for AED pharmacokinetic evaluation if clinically indicated
- Record AESI
- Collect used, partially used and unused study medication; perform drug accountability and review with parent/caregiver
- Dispense study medication

At Clinic Visit 10, compliant subjects who have tolerated IMP should be presented with the ICF for the open-label extension (Part 2). Informed consent for the open-label extension should be signed at Visit 12 or earlier in order to enter the open-label extension.

6.1.2.8 Phone Visit 11 (Maintenance Period Study Day 85)

Site personnel will contact the subject via telephone on Maintenance Period Study Day 85 and record the following:

- AEs
- AESI
- Concomitant Medications

In addition, site personnel will review the diary entries with the parent/caregiver. Ensure diary is being completed daily; if diary compliance is low (i.e. <90%), re-train parent/caregiver.

6.1.2.9 Clinic Visit 12 (Maintenance Period Study Day 99): End of Study/Early Termination

The End-of-Study participation in Part 1 for an individual subject occurs after he/she has received IMP for 12 weeks in the Maintenance Period. At the Part 1 End-of-Study visit, the

ZX008 (Fenfluramine Hydrochloride)
ZX008-1601 Clinical Study PA 4.0 (Japan) 25 July 2022

subject may enroll into the Part 2 OLE Treatment Period if they have completed 12 weeks of treatment in the Maintenance Period. Other circumstances for participation in Part 2 are described in [Section 4.3](#). Informed consent for the Part 2 OLE Treatment Period should be signed before data collection begins on Visit 12 (if not signed earlier) in order to participate in Part 2.

The End-of-Study visit may also occur if the subject withdraws participation from the study or the sponsor terminates the study. If the subject withdraws participation from the study, they may on a case-by-case basis, be eligible for entrance into the Part 2 OLE Treatment Period after consideration of the circumstances of the early termination and the potential benefit-risk of continued participation in a ZX008 trial. The decision whether to permit Part 2 participation resides solely with the sponsor, who may consult with the site investigator. If the sponsor terminates the study early, the subject may or may not be offered enrollment into Part 2, depending on the reason for termination.

Subjects will visit the clinic for the End-of-Study visit if one the following events occur:

1. The subject withdraws or is withdrawn from participation in the study.
2. The sponsor terminates the study.
3. The subject completes all study related visits and

procedures. The following procedures will be performed:

- Review current seizure activity (number/type/duration) from diary since previous visit
- Record concomitant medications
- Complete physical examination, including height and weight
- Complete neurological examination
- Obtain vital signs
- 12-lead electrocardiogram
- Doppler ECHO (must be performed any time between Study Day 90 and Study Day 113; if subject terminates early from the study, the ECHO should be scheduled as soon as practical). If the Study Day 43 ECHO was completed ≤ 30 days prior to early termination, the Visit 12 ECHO will not be performed provided the parent/guardian agrees to bring the subject to the clinic for the cardiac follow-up visit (see [Table 9](#)).
- Urine or serum pregnancy test for females of child-bearing potential
- Laboratory evaluation (serum chemistry, hematology, immunoglobulin, hormones, and urinalysis (urine for urinalysis may be collected at home, the night before the clinic visit, as long as collection procedures are followed to maintain sample stability))
- Urine or serum THC panel
- Whole blood CBD
- Collect plasma sample for AED pharmacokinetic evaluation (must document time of last dose)
- Tanner Staging for subjects >7 to 18 years of age ([Appendix 5](#))
- Collect, review, and dispense diary. Ensure diary is being completed daily; if diary compliance is low (i.e. $<90\%$), re-train parent/caregiver
- C-SSRS Since Last Visit Assessment ([Appendix 2](#))
- Clinical Global Impression – Improvement (assessed by parent/caregiver)

ZX008 (Fenfluramine Hydrochloride)
ZX008-1601 Clinical Study PA 4.0 (Japan) 25 July 2022

- Clinical Global Impression – Improvement (assessed by investigator)
- BRIEF ([Appendix 3](#))
- QOLCE ([Appendix 6](#))
- HADS ([Appendix 7](#))
- Zarit Caregiver Burden Inventory ([Appendix 8](#))
- Record AEs
- Record AESIs
- Collect used, partially used and unused study medication; perform drug accountability and review with parent/caregiver
- Dispense study medication for taper for subjects not continuing into Part 2.
- Dispense and administer study medication for transition for subjects continuing into Part 2. Subjects will be required to stay in the clinic for monitoring of adverse reactions until the investigator determines it is safe to leave. Those considered by the investigator to need further monitoring will be hospitalized until the investigator determines they can be safely discharged.

6.1.3 POST-DOSE VISIT (CLINIC VISIT 13; STUDY DAY 113)

For subjects entering the Part 2 OLE Treatment Period, the subject will visit the clinic on Day 113, which will also be Part 2 Day 1. The procedures described in [Section 6.2](#) will be followed.

If the subject does not enter the Part 2 OLE Treatment Period (or discontinues from the study early), the subject will visit the clinic on Study Day 113 (or 14 days after the day of discontinuation). If necessary, Visit 13 may be conducted as a phone call, provided diaries and study medication are returned by this time. The following will be recorded/performed:

- Review current seizure activity (number/type/duration) from diary since previous visit
- AEs
- AESIs
- Concomitant medications
- Collect and review diary with parent/caregiver
- Collect used, partially used and unused study medication; perform drug accountability and review with parent/caregiver

6.1.4 CARDIAC FOLLOW-UP VISIT (CLINIC VISIT 14; 3 and 6 months after last dose)

If the subject completes the study but does not enter the Part 2 OLE Treatment Period or discontinues from the study early, the subject will return to the clinic after study drug discontinuation for follow-up cardiac testing. The timing and frequency of exams are in Table 10. Subjects on blinded medication who are found to have been on placebo are not required to participate in follow-up testing once the blind is broken. As the ECHO and ECG will be administered in a separate clinic than the pediatric neurology clinic, an asymptomatic subject receiving a follow-up ECHO and ECG does not require a physical examination.

Subjects with positive findings on safety evaluations at post-dose follow-ups should have

ZX008 (Fenfluramine Hydrochloride)
ZX008-1601 Clinical Study PA 4.0 (Japan) 25 July 2022

repeat examinations every 3 months until the finding is resolved or stable and unlikely to change, with reports submitted as AEs to the ZX008 safety database.

Table 10: Schedule of Post-Treatment Cardiac Follow-up for Part 1

| Parameter | Duration of Blinded ^a or Fenfluramine Treatment | | | Have had any cardiac sign or symptom regardless of the time on study drug ^b |
|--|--|------------------------------|------------------------------------|---|
| | Less than 2 weeks Cumulative | 2 and <13 weeks | >13 weeks | |
| ECHO | No | Yes, 3 months post-treatment | Yes, 3 and 6 months post-treatment | Yes, 3 and 6 months post-treatment, and every 3 months until resolved, or stable and unlikely to change |
| ECG | No | Yes, 3 months post-treatment | Yes, 3 and 6 months post-treatment | Yes, 3 and 6 months post-treatment and every 3 months until resolved, or stable and unlikely to change |
| Physical examination | No | Yes, 3 months post-treatment | Yes, 3 months post-treatment only | Yes, 3 and 6 months post-treatment, and every 3 months until resolved, or stable and unlikely to change |
| ^a If blind is broken at the end of the study and a subject revealed to have taken only placebo, no further testing is required. ^b Positive sign or symptom includes any development of valve thickening or regurgitation ("trace" or greater in mitral, aortic; mild or greater in pulmonary, tricuspid), or sign or symptom indicative of potential pulmonary hypertension as adjudicated by the ICAB. | | | | |

6.2 Part 2

Review of inclusion and exclusion criteria and written informed parental or guardian consent and assent of minors (if the subject is capable of providing assent) for Part 2 must be obtained before a subject can start any of the Part 2 Visit 15 procedures. This includes review and approval (or adjudication if required) of the ECG and/or ECHO findings by the central reader, and approval for continuation in the open-label extension (if applicable) by the IDSMC.

Only eligible subjects as specified by the inclusion and exclusion criteria who have successfully completed Part 1, or have permission from the Sponsor, will be enrolled into Part 2. Other circumstances for participation in Part 2 are described in Section 4.3.

Study procedures for the Part 2 OLE Treatment Period will be conducted according to the Schedule of Assessments in Table 2. Time windows for all assessments are detailed in Table 11.

ZX008 (Fenfluramine Hydrochloride)**ZX008-1601 Clinical Study PA 4.0 (Japan) 25 July 2022****Table 11: Time Windows for Assessments in Part 2**

| Visit / Procedure | Time window (relative to scheduled visit / procedure) |
|---|---|
| Visit 15 (Clinic; OLE Study Day 1) | ± 4 days ^a |
| Visits 16 (Clinic/Phone; OLE Study Day 15) | ± 3 days |
| Visits 17-41 (Clinic; OLE Study Days 30, 60, 90, 180, 270, 360, 450, 540*, 630, 720*, 810, 900*, 990, 1080*, 1170, 1260*, 1350, 1440*, 1530, 1620*, 1710, 1800*, 1890, 1980*, 2070) | ± 4 days |
| Visit 42 (Clinic; OLE Study Day 2160; EOS) | ± 4 days |
| Visit 43 (Clinic; OLE Study Day 2174; post dosing) | ± 4 days |
| Visit 44, 45 (ECHO clinic; 3 and 6 months after last dose) | + 30 days |

AED=antiepileptic drug (s); ECHO=echocardiogram

^a In the case of a required safety review of a Visit 12 ECHO alert, the transition period between Visit 12 and Visit 15 may be extended up to 14 days to allow time for adjudication.

*If marketing approval is not yet received after the end of the OLE Treatment Period, treatment may be extended on an annual basis in order to provide continuity of treatment for subjects who are enrolled in Part 2 of the study. Up to 5 annual extensions can be applied, for a total treatment time of 72 months in the OLE. Continuation will be based on review of safety/tolerability and effectiveness, and be offered for subjects who continue to meet eligibility requirements, comply with investigator's instructions, and for whom the investigator judges benefit outweighs risk. The decision to extend and informed consent should be completed before the start of the first visit of the extension (e.g. Month 12, 24, 36, 48 or 60). After approval from Investigator and Sponsor for extension and starting after Visit 26/ Month 24 (or at a later visit if Visit 26/ Month 24 visit has already occurred at the time of Protocol Amendment 4.0 approval), subject will return to the clinic every 6 months for the 1 year extension (i.e. Month 30, 36). The End of Study will be Visit 42, unless another extension is granted, in which case the subject will continue to return for clinic visits every 6 months and will have a phone visit 3 months after the in-clinic visit. Further extensions can then be applied as required if marketing approval is not yet received.

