Part 1 will consist of a 4-week baseline, 2-week titration, 12-week maintenance, and 2-week taper or transition period. The 4-week Baseline Period will consist of the establishment of initial eligibility during a screening visit to include an assessment of cardiac parameters (ECG and ECHO), followed by an observation period where subjects will be assessed for baseline seizure frequency based on recordings of daily seizure activity entered into a diary. Upon completion of the Baseline Period, subjects who qualify for the study will be randomized (1:1:1) in a double-blind manner to receive 1 of 2 doses of ZX008 (0.2 mg/kg/day, 0.8 mg/kg/day; maximum dose: 30 mg/day [or 0.5 mg/kg/day, maximum 20 mg/day, for subjects taking concomitant stiripentol (STP)]) or placebo. Randomization will be stratified by weight (<37.5 kilograms [kg], ≥37.5 kg) to ensure balance across treatment arms, and at least 25% of subjects will be in each weight group. All subjects will be titrated to their blinded randomized dose over a 2-week Titration Period. Following titration, subjects will continue treatment at their randomly assigned dose over a 12-week Maintenance Period. Total treatment time from the beginning of the Titration Period through the end of the Maintenance Period is 14 weeks. Subjects will have ECG and ECHO assessments at weeks 6 and 14 during the Maintenance Period. At the end of the Maintenance Period (or early discontinuation), all subjects will undergo a blinded 2-week taper or transition period (Post-Dosing Follow-Up) depending on whether they exit the study or are enrolled in Part 2, the long-term open-label extension, respectively. A follow-up ECG and ECHO will be performed 3-6 months after study drug discontinuation for early termination, or for those subjects who complete the study but do not enter the open-label extension part. If there are any findings at the 3-month post-dose follow-up, a second follow-up will be repeated at 6 months and then every 3 months until resolved or stabilized.

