5.5.5 Part 1: Transition Period

Subjects who complete the Maintenance Period and will be continuing into the open-label extension (Part 2) will be transitioned from double-blind study medication to open-label ZX008 (Table 7).

All subjects entering the open-label extension (Part 2) will be transitioned from their blinded daily dose to the 0.2 mg/kg dose during the 2-week interval between Visits 12 and 15, without breaking the blind. The IWR system will assign two bottles of IMP to the subject, one for each step in the transition. A new bottle of IMP will be started by the subject at each level of the transition step. See Section 5.1 for more information about the volume of ZX008 or placebo to be administered.

Table 7: Transition Algorithm for Part 1

| Dose Group in Double-Blind Study | Transition Step 1 Day 1-4 after Visit 12 | Transition Step 2 Days 5-14 after Visit 12 |
|---|---|---|
| ZX008 0.2 mg/kg/day | ZX008 0.2 mg/kg/day | ZX008 0.2 mg/kg/day |
| ZX008 0.8 mg/kg/day (0.5 mg/kg/day for subjects taking concomitant STP) | ZX008 0.4 mg/kg/day | ZX008 0.2 mg/kg/day |
| Placebo | ZX008 0.2 mg/kg/day | ZX008 0.2 mg/kg/day |

Note: maximum daily dose of ZX008 is 30 mg (or 20 mg for subjects taking concomitant STP).

Subjects who had been randomized to placebo increase their dose to 0.2 mg/kg/day beginning on Day 1 of the transition. The first dose should be taken in the clinic during Visit 12. Subjects will be required to stay in the clinic for monitoring of adverse reactions until the investigator determines it is safe to leave. Those considered by the investigator to need further monitoring will be hospitalized until the investigator determines they can be safely discharged. Subjects who had been randomized to 0.2 mg/kg/day will continue to receive that dose. Subjects who had been randomized to 0.8 mg/kg/day or were receiving the maximum dose of 30 mg/day (or subjects taking concomitant STP and randomized to 0.5 mg/kg/day; 20 mg/day maximum) decrease to a dose of ZX008 0.4 mg/kg/day, or a maximum of 30 mg/day (20 mg/day for subjects taking concomitant STP). After 4 days at this dose level (Day 5), these subjects will decrease their dose to 0.2 mg/kg/day. Subjects will report to the clinic on Day 14 for enrollment into the open-label extension.

ZX008 (Fenfluramine Hydrochloride)
ZX008-1601 Clinical Study PA 4.0 (Japan) 25 July 2022

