6. VISIT SCHEDULE

6.1 Part 1

Study procedures for the Part 1 Double-blind Treatment Period will be conducted according to the Schedule of Assessments in Table 1. Time windows for all assessments in Part 1 are detailed in Table 9

Table 9: Time Windows for Assessments in Part 1

| Visit / Procedure | Time window (relative to scheduled visit / procedure) |
|---|---|
| Visit 1 (Clinic; Study Day -29 to -28 or -28 to -27): | Not applicable |
| Visit 2 (Phone; Study Day -15) | ± 3 days |
| Visit 3 (Clinic; Study Day -1; Randomization) | + 4 days ^a |
| Visits 4, 5 (Phone; Study Days 4, 8) | ± 3 days |
| Visit 6 (Clinic; Study Day 15) | ± 4 days |
| Visit 7 (Phone; Study Day 29) | ± 4 days |
| Visit 8 (Clinic; Study Day 43) | ± 4 days |
| Visit 9 (Phone; Study Day 57) | ± 4 days |
| Visit 10 (Clinic; Study Day 71) | ± 4 days |
| Visit 11 (Phone; Study Day 85) | ± 4 days |
| Visit 12 (Clinic; Study Day 99) | ± 4 days |
| Visit 13 (Clinic; Study Day 113; post dosing) | ± 4 days |
| Visit 14 (ECHO clinic; 3-6 months after last dose) | + 30 days |
| Blood collection for ZX008 PK | ± 15 minutes |

AED=antiepileptic drug (s); ECHO=echocardiogram; PK = pharmacokinetics

a In cases where the screening period is extended beyond 28 days, the immediate 28 days before the Randomization visit will be used to calculate the baseline seizure frequency

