8.9 FOLLOW-UP OF ADVERSE EVENTS

Every effort should be made to follow-up subjects who continue to experience an AE or an SAE on completion of the study or until the AE resolves. All follow-up information (and attempted follow-up contacts) should be documented in the subject's medical records. Details of the subject's progress should also be submitted to the sponsor/designee's Global Clinical Safety and Pharmacovigilance and the Medical Monitor.

Subjects who are discontinued from the study or complete the study and have been found to have any signs of valvulopathy or pulmonary hypertension on ECHO will be followed until the condition has resolved or stabilized where no further changes are likely, for a minimum of 6 months from the last dose of study medication, unless it is determined after unblinding that the subject did not receive ZX008.

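### Section 6.1.4 words the placebo waiver of cardiac follow-up more widely than Table 10 note a, and read literally it releases placebo-arm subjects given ZX008 in the transition

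*Protocol*

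**What the plan says.** Section 6.1.4 governs the cardiac follow-up visit for subjects who finish Part 1 without entering Part 2 and for those who stop early. It sends the reader to Table 10 with the words "The timing and frequency of exams are in Table 10". The next sentence waives testing for subjects on blinded medication who are "found to have been on placebo are not required to participate in follow-up testing once the blind is broken".

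Table 10 sits in the same section. Its duration header begins "Duration of Blinded", with note a attached, and goes on to fenfluramine treatment as the alternative. For a blind broken at the end of the study, note a provides that, for "a subject revealed to have taken only placebo, no further testing is required".

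Section 8.9 covers subjects with ECHO signs of valvulopathy or pulmonary hypertension. They are followed until the condition resolves or stabilises, and for at least 6 months after the last dose, "unless it is determined after unblinding that the subject did not receive ZX008".

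Section 5.5.5 describes the transition: "Subjects who had been randomized to placebo increase their dose to 0.2 mg/kg/day beginning on Day 1 of the transition". Table 7 keeps them on that dose for the 14 days, and the blind is maintained throughout.

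The synopsis, under Duration of Treatment, waives follow-up for a subject known to be taking placebo because the blind was broken. Section 3.3 and Table 1 note c contain no placebo waiver.

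**The concern.** Note a and Section 8.9 turn on exposure: did the subject ever receive ZX008? The sentence in Section 6.1.4 turns on having been on placebo, which is also true of a placebo-arm subject who took placebo for 14 weeks and then ZX008 in the transition. Such a subject has been on placebo but has not taken only placebo.

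The protocol requires ECHO and ECG after the last dose because fenfluramine was withdrawn from the market after reports of heart valve disease and pulmonary hypertension. At stake is whether a site following the section that governs the visit could properly skip that testing for someone whose last doses were active drug. No endpoint, analysis or sample size depends on it.

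**Working it through.** The plan gives no figure to reproduce. The check sets the waivers side by side, asks whether the case can arise, and then works out which column of Table 10 would apply.

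**1. The waivers applied to one subject:** placebo arm, ZX008 taken in the transition, Part 2 not entered, blind broken.

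| Place | Condition for no follow-up | Is this subject released? |
|---|---|---|
| Section 6.1.4, text | found to have been on placebo | Yes, read literally |
| Table 10, note a | took only placebo | No |
| Section 8.9 (ECHO signs only) | did not receive ZX008 | No |
| Synopsis, Duration of Treatment | known to be taking placebo | Unclear |
| Section 3.3; Table 1 note c | no placebo waiver | No |

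The pointer to Table 10 covers the timing and frequency of examinations. The waiver that follows is a sentence of its own, so the pointer does not expressly narrow it.

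**2. Can the case arise?**
- Section 6.1.2.9 allows the Visit 12 ECHO up to Day 113, whereas transition dosing starts at Visit 12, nominally Day 99. Section 6.2 requires ECG/ECHO review, and IDSMC approval if applicable, before Visit 15 procedures. Eligibility can therefore be settled after ZX008 has been taken.
- Under Section 5.5.1.1 blinding extends through the transition, and a subject whose blind is broken is discontinued.
- Under Section 4.5 a subject may withdraw at any time.

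Each route can lead to a placebo-arm subject exposed to ZX008 who does not enter Part 2.

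**3. Testing at stake on total blinded time (Part 1 completers).** Table 9 gives "Visit 12 (Clinic; Study Day 99"), ± 4 days.
- Earliest: 99 − 4 = Day 95; 95 / 7 = 13.6 weeks.
- Latest: 99 + 4 = Day 103; 103 / 7 = 14.7 weeks.
- Cut-off: 13 × 7 = 91 days, and 95 > 91.
- After the nominal transition: 99 + 14 = Day 113; 113 / 7 = 16.1 weeks.

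A completer is therefore in the column above 13 weeks across the whole Visit 12 window: ECHO and ECG at 3 and 6 months.

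**4. Testing at stake on fenfluramine time alone.**
- Nominal transition: 14 / 7 = 2.0 weeks.
- With the extension of up to 14 days for a Visit 12 ECHO alert (Table 11 note a): (14 + 14) / 7 = 4.0 weeks.

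Both values fall in the column that starts at 2 weeks: one ECHO and one ECG, at 3 months. A subject who stops before 14 days is in the column below 2 weeks, which requires neither unless there is a cardiac sign or symptom.

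**The case against.** The strongest reply is that Section 6.1.4 already contains the right rule. Note a stands in the same section, in the table that sets who is tested and when, and a specific note is naturally read as qualifying a summary sentence. The sentence can also be read more narrowly: the transition bottles are blinded medication too, and a subject whose bottles held ZX008 is not plainly found to have been on placebo. Both points stand in part. A careful site could reach the right answer, and loss of follow-up is not inevitable. But the two wordings still differ on a safety procedure, and nothing in the text says which prevails.

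The reply also limits the size, and this stands. Subjects known at Visit 12 not to be continuing get taper drug, which is placebo throughout for the placebo arm (Table 6), so the usual placebo-arm subject in Section 6.1.4 is unexposed. Breaking the blind is restricted to cases where treatment depends on it. The most plausible cardiac route, an ECHO alert adjudicated against continuation, leads to subjects whom Section 8.9 covers if they show signs of valvulopathy or pulmonary hypertension. This amendment is aimed mainly at subjects remaining in Part 2 in Japan, so few or none may still pass through the transition, although the text does not say that Part 1 is closed.

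A reader might infer that two ECHOs and two ECGs are necessarily lost per subject. The documents do not support that: the Table 10 header names blinded or fenfluramine treatment without saying which counts once the blind is broken, and on fenfluramine time the loss is one of each or none.

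**Conclusion.** The concern holds as a minor conflict of wording with a safety consequence. Read literally, Section 6.1.4 releases an unblinded placebo-arm subject who received ZX008 in the transition and did not enter Part 2; note a to Table 10 does not.

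The number affected is very small and may be zero; the protocol gives nothing from which to estimate it. Per subject, the testing at stake ranges from none (under 14 days of ZX008, fenfluramine time) through one ECHO and one ECG (at least 14 days, fenfluramine time) to two of each (total blinded time, for a Part 1 completer). The conclusion assumes only that a site applies the sentence as written without narrowing it by note a.

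Two wider inferences are not supported. A reader might conclude that exposed subjects with valve findings would go unfollowed; Section 8.9 prevents that. A reader might also think that Section 3.3 and Table 1 note c share the fault; they carry no waiver, so they default to follow-up and leave no gap.

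**What to change.** In Section 6.1.4, limit the waiver to subjects revealed on unblinding to have taken only placebo, including during the transition, so that no ZX008 was received. This brings the sentence into line with note a. Make the same change in the synopsis under Duration of Treatment, where the wording is ambiguous for this subject. Section 3.3, Table 1 note c and Section 8.9 can stay as they are, and this point requires no change to how Table 10 counts time.

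The cost is one clause in two places. It adds no testing beyond what Table 10 already requires.
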